6.12.6. Vital Signs and Other Physical Findings

Postbaseline measurements and change from baseline to postbaseline for vital signs and physical characteristics (systolic blood pressure [SBP], diastolic blood pressure [DBP], pulse rate, weight, BMI) at the scheduled visits will be summarized for patients who have both baseline and at least 1 postbaseline result.

The measurements during the treatment period (0 to 26, 0 to 52 weeks) will be analyzed by an MMRM model with treatment, baseline value of the response variable, visit, and visit by treatment interaction as fixed factors and patient as the random factor.

Weight during the lead-in period will also be analyzed by an MMRM model with Visit 2 value of the response variable, randomized treatment, visit, and treatment-by-visit interaction as fixed factors and patient as the random factor in all randomized patients.

An ANCOVA model will also be used for the analysis of the last nonmissing observation (including early discontinuation) during the treatment period and during the entire study (up to Visit 801). The ANCOVA models are the same as those used for clinical laboratory measures.

Change from the minimum value during the baseline period to the minimum value during the treatment period (0 to 26, 0 to 52 weeks) for vital signs and physical characteristics will be summarized for patients who have both baseline and at least 1 postbaseline result. Baseline will be the minimum of nonmissing observations in the baseline period. The minimum value in the treatment period will be analyzed. Similarly, change from the maximum value during the baseline period to the maximum value during the treatment period (0 to 26, 0 to 52 weeks) for vital signs and physical characteristics will be summarized for patients who have both baseline

and at least 1 postbaseline result. Baseline will be the maximum of nonmissing observations in the baseline period. The maximum value in the treatment period will be analyzed.

The percentages of patients with treatment-emergent high or low vital signs and weight at any time during the treatment period (0 to 26, 0 to 52 weeks) or during the entire study including safety follow-up period will be summarized by treatment group (0 to 26: all 3 treatment groups; 0 to 52: only the 2 double-blind treatment groups) for patients who have both baseline and at least 1 postbaseline measurement. A treatment-emergent high result is defined as a change from a value less than or equal to the high limit at all baseline visits to a value greater than the high limit at any time that meets the specified change criteria during the treatment period or during the entire study including safety follow-up period. A treatment-emergent low result is defined as a change from a value greater than or equal to the low limit at all baseline visits to a value less than the low limit at any time that meets the specified change criteria during the treatment period or during the entire study including safety follow-up period. Treatment comparison will be based on Fisher's exact test. Table 6.7 will be used to define the low and high limits and change thresholds.

Table 6.7. Categorical Criteria for Abnormal Treatment-Emergent Blood Pressure and Pulse Measurement, and Categorical Criteria for Weight Changes for Adults

Parameter	Low	High
Systolic BP (mm Hg) (Supine or sitting – forearm at heart level)	≤ 90 and decrease from baseline ≥ 20	≥ 140 and increase from baseline ≥ 20
Diastolic BP (mm Hg) (Supine or sitting – forearm at heart level)	≤ 50 and decrease from baseline ≥ 10	≥ 90 and increase from baseline ≥ 10
Pulse (bpm) (Supine or sitting)	< 50 and decrease from baseline ≥ 15	> 100 and increase from baseline ≥ 15
Weight (kg) (Consistent clothing and timing in relationship to meals and voiding)	(Loss) decrease $\geq 7\%$	(Gain) increase $\geq 7\%$

Abbreviations: BP = blood pressure.

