A restricted maximum likelihood based, mixed-effect model repeated measure (MMRM) analysis will be used to analyze continuous longitudinal variables. All the longitudinal observations at each scheduled postbaseline visit will be included in the analysis. The model for the analysis of the primary efficacy endpoint of change from baseline in HbA1c will include the fixed class effects of treatment, strata (pooled country, type of basal insulin, and prandial insulin dosing plan), visit, and treatment-by-visit interaction, as well as the continuous, fixed covariate of baseline value. For analyses of variables other than HbA1c, the HbA1c stratum ($\leq 7.5\%$, $>7.5\%$) will be included in the model. An unstructured covariance structure will be used to model the within-patient errors. Significance tests will be based on least squares (LS) means and Type III tests. SAS PROC MIXED will be used to perform the analysis. If this analysis fails to converge, the following covariance structures will be tested in order:

- Toeplitz with heterogeneity
- Autoregressive with heterogeneity
- Compound symmetry with heterogeneous variances
- Toeplitz
- Autoregressive
- Compound symmetry without heterogeneous variances.

The first covariance structure that converges will be used. The Kenward-Roger approximation will be used to estimate denominator degrees of freedom.

Analysis of covariance (ANCOVA) will also be used to analyze continuous variables. The model for the change from baseline to the Week 26 HbA1c endpoint will include treatment and strata (pooled country, type of basal insulin, and prandial insulin dosing plan) as fixed effects and baseline as a covariate. Unless otherwise stated, missing endpoints will be imputed using the last-observation-carried-forward (LOCF) approach, using only postbaseline data. For analyses of variables other than HbA1c, the HbA1c stratum ($\leq 7.5\%$, $>7.5\%$) will be included in the model.

For continuous measures, summary statistics will include sample size, mean, SD, median, minimum, and maximum for both the actual and the change from baseline measurements. LS means and standard errors derived from the analysis models will also be displayed for the change from baseline measurements. Treatment comparisons will be displayed showing the treatment difference LS means and the 95% CIs for the treatment differences, along with the p-values for the treatment comparisons.

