Hypoglycemia rates will be summarized for periods of 30 days, 1 year, and 100 years (severe hypoglycemia only). The rate of severe hypoglycemia per 100 years will be compared between treatment groups using the empirical method (details will be described in SAP). For each of the other categories of hypoglycemia, the number of hypoglycemia events during a specific period (rate) after randomization (for example, Weeks 0-12 of treatment period) will be analyzed by using a negative binomial regression model. The model will include treatment and the baseline hypoglycemia rate (measured during lead-in) as a covariate. An offset defined as the log transformation of treatment exposure in the specific period (days)/365.25 days (or 30 days) will be included in the model to estimate the rate of hypoglycemia per year (or per 30 days). The proportion of patients with at least 1 hypoglycemic event in each category (incidence) during a specific period after randomization will be analyzed using a logistic regression model including treatment and baseline hypoglycemia rate value in the model.

Continuous safety variables, as well as the change from baseline for these variables, will be analyzed by MMRM or ANCOVA models. For categorical variables, Fisher's exact test or Pearson's chi-square test will be used to compare treatment groups unless otherwise specified.

The analyses for assessing immunogenicity data will be described in the SAP after being agreed with the FDA on the threshold for determining treatment-emergent antibodies to insulin lispro.

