14. To compare LY900014, LY900014+20, and insulin lispro with respect to diabetes treatment satisfaction as measured by the ITSQ	14. Change from baseline in ITSQ regimen inconvenience and lifestyle flexibility domain scores at Week 26 and Week 52
15. To compare LY900014, LY900014+20, and insulin lispro with respect to the proportion of patients achieving HbA1c targets	15. The proportion of patients with HbA1c <7% and ≤6.5% at Week 26 and Week 52
16. To compare the glycemic control of LY900014 and insulin lispro	16. Actual and change from baseline to Week 52 in HbA1c
Tertiary/Exploratory Objectives	
17. To compare the safety of LY900014, LY900014+20, and insulin lispro	17. Adverse events, vital signs, chemistry, and hematology laboratory measures
18. To compare the incidence of treatment-emergent positive anti-insulin lispro antibodies for LY900014, LY900014+20, and insulin lispro	18. Incidence of treatment-emergent positive anti-insulin lispro antibodies

Objectives and Endpoints

Objectives	Endpoints
Tertiary/Exploratory Objectives (continued)	
21. To compare LY900014, LY900014+20, and insulin lispro with respect to changes in body weight	21. Change in weight (kg) from baseline to Week 26 and Week 52
22. To compare LY900014, LY900014+20, and insulin lispro with respect to the proportion of patients achieving improvement from baseline in HbA1c targets	22. The proportions of patients with shifts in HbA1c to <8% and ≤9%, and >9% from baseline to Week 26 and Week 52
23. To compare LY900014, LY900014+20, and insulin lispro with respect to glycemic variability	23. Within-day and between-day glycemic variability measured by the standard deviation and the coefficient of variation of 10-point SMBG profiles

Abbreviations: 1,5-AG = 1,5-Anhydroglucitol; CCI

HbA1c = hemoglobin A1c; ITSQ = Insulin Treatment Satisfaction Questionnaire; MMTT = mixed-meal tolerance test; NIM = noninferiority margin; PPG = postprandial glucose; SMBG = self-monitored blood glucose; T1D = type 1 diabetes mellitus; CCI

5. Study Design

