The total daily basal insulin dose, total daily prandial insulin dose, total insulin dose, and the ratio of prandial insulin dose to total insulin dose during the lead-in period will be summarized by visit for the Randomized Population. The actual and change from Visit 2 values will be compared between treatment groups using an MMRM model including the corresponding dose at Visit 2, treatment, strata (pooled country, type of basal insulin, prandial insulin dosing plan, and HbA1c stratum), visit, treatment-by-visit interaction in the model as fixed factors and patient as a random factor. Doses will be summarized in U and U/kg. Basal insulin dose will be summarized independently for glargine and degludec as well as combined.

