Both actual and change from baseline (Visit 2) for the anti-insulin lispro antibody level in percent binding will be summarized by scheduled visit prespecified in the protocol for patients with positive TEADA response during the treatment period of 0 to 26 weeks. The repeated measurement from Visit 2 to Visit 18 will be analyzed by an MMRM model with treatment, baseline value of the response variable, visit, and visit by treatment interaction as fixed factors and patient as the random factor. The ANCOVA model using treatment and baseline value as covariates will be used for the analysis of maximum percent binding during the treatment period of 0 to 26 weeks. A similar summary of antibody level in percent binding during the analysis period of Visit 2 to Visit 801 will be generated separately for the 2 double-blind treatment groups and the open-label treatment group.

A listing of anti-insulin lispro antibody at each visit will be provided. The listing will include anti-insulin lispro antibody status (detected/not detected), anti-insulin lispro antibody percent binding, TEADA status (positive/negative), insulin cross-reactivity status, insulin cross-reactivity percent binding for the safety population.

Subgroup analysis for the following selected efficacy and safety variables will be performed by the TEADA status during the treatment period of 0 to 26 weeks:

- Use data prior to discontinuation of IP:
 - HbA1c and change from baseline in HbA1c
 - 1-hour and 2-hour PPG excursions
 - basal, prandial, and total insulin dose
 - event rate (per patient per year) of overall hypoglycemic events
- Use all data regardless of IP use:
 - treatment-emergent injection site reaction and hypersensitivity reaction

The analyses for HbA1c and change from baseline in HbA1c will be performed using an MMRM model for the primary analysis and the HbA1c data prior to discontinuation of IP. The model will include additional fixed terms of subgroup, subgroup by treatment interaction, subgroup by visit interaction, and 3-way interaction of treatment, subgroup, and visit.

The PPG excursions will be analyzed by the ANCOVA model same as the model specified in Section 6.11.2 using the efficacy estimand. The model will include additional terms of subgroup, subgroup by treatment interaction, subgroup by visit interaction, and 3-way interaction of treatment, subgroup, and visit.

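### SAP 6.12.6 fits the weight and vital-sign MMRM with a random patient factor and no stated covariance structure, where Protocol 10.3.1 specifies unstructured errors

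*SAP*

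**What the plan says.** Protocol 10.3.1 sets the general rule. A "mixed-effect model repeated measure (MMRM) analysis will be used to analyze continuous longitudinal variables", and "An unstructured covariance structure will be used to model the within-patient errors". An ordered list of fallback structures follows in case of non-convergence, ending with equal-variance compound symmetry. Kenward-Roger degrees of freedom are specified. Protocol 10.3.4 adds: "Continuous safety variables, as well as the change from baseline for these variables, will be analyzed by MMRM or ANCOVA models". That sentence neither repeats the covariance structure nor refers back to 10.3.1.

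SAP 6.11.1 restates the unstructured covariance, the fallback list and Kenward-Roger for HbA1c, with no random patient term. SAP 6.11.5 carries that model over to 1,5-AG, SMBG and on-treatment insulin dose by calling their model similar to the primary one.

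SAP 6.12.6 words the model for blood pressure, pulse, weight and BMI differently. It is called an MMRM with treatment, "baseline value of the response variable, visit, and visit by treatment interaction as fixed factors and patient as the random factor". No covariance structure, fallback, degrees-of-freedom method or cross-reference is given. The same form appears in SAP 6.12.7.1 for antibody percent binding ("visit, and visit by treatment interaction as fixed factors and patient as the random factor") and in SAP 6.10 for lead-in insulin dose ("treatment-by-visit interaction in the model as fixed factors and patient as a random factor").

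Weight is tertiary/exploratory objective 21 in SAP Table 4.1: "Change in weight (kg) from baseline to Week 26 and Week 52". SAP 6.12.6 plans a second analysis: "An ANCOVA model will also be used for the analysis of the last nonmissing observation (including early discontinuation) during the treatment period".

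**The concern.** A programmer working from SAP 6.12.6 alone would most naturally code a random patient intercept with independent residuals. That is equal-variance compound symmetry, the last resort in the plan's own fallback list. It forces one variance on every visit.

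Weight is measured from Week 2 onwards, and the spread of change from baseline may well grow with time on treatment. If it does, the early visits pull the common variance below the variance at the endpoint visit. The Week 26 and Week 52 intervals for weight would then be too narrow and their p-values too small. SAP 6.5 makes no multiplicity adjustment for objectives of this kind, so each nominal interval has to be sound on its own.

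Insulin dose is also specified one way during lead-in (SAP 6.10) and another way on treatment (SAP 6.11.5), with no reason given.

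**Working it through.** The documents state no SD, standard error or power for weight, so there is no figure of the plan's to reproduce. The size has to be shown over assumed variance paths.

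**Inputs**
- Post-randomization weight visits (Protocol Section 2): Weeks 2, 4, 8, 12, 18, 22, 26, then 32, 39, 46, 52 for the double-blind arms.
- Two-sided level 0.05 (SAP 6.1).
- 436 randomized and about 371 completers per double-blind arm, 15% dropout to Week 26 (Protocol 10.1).
- Assumed: how the SD of weight change, given baseline, moves over visits.

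**Formula.** Let v_t be the variance at visit t, v̄ its mean over visits and v_L its value at the last visit. With complete data and a treatment effect at each visit, the random-intercept model gives every visit contrast the standard error sqrt(2v̄/n). The correct value at the last visit is sqrt(2v_L/n). So

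r = model SE / correct SE = sqrt(v̄ / v_L), and actual error rate = 2 × [1 − Φ(1.96 r)].

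**Worked case: SD doubles linearly from Week 2 to Week 26.** With a starting SD of 1, the SDs are 1, 1.083, 1.25, 1.417, 1.667, 1.833 and 2. The squares sum to 15.88, so v̄ = 15.88/7 = 2.269 and v_L = 4. Then r = sqrt(2.269/4) = 0.753, 1.96 × 0.753 = 1.476, and the error rate is 0.140.

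**Range** (SD linear from the first to the last visit)

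| SD at last visit / first visit | r, Week 26 | error rate | r, Week 52 | error rate |
|---|---|---|---|---|
| 0.9 | 1.06 | 0.038 | 1.06 | 0.037 |
| 1 (constant) | 1.00 | 0.050 | 1.00 | 0.050 |
| 1.25 | 0.90 | 0.079 | 0.89 | 0.081 |
| 1.5 | 0.83 | 0.104 | 0.82 | 0.109 |
| 2 | 0.75 | 0.140 | 0.74 | 0.150 |
| 3 | 0.69 | 0.180 | 0.66 | 0.196 |

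For variance proportional to time, v̄/v_L is mean visit week over last week. At Week 26 this is (92/7)/26 = 13.1/26, so r = 0.71 and the error rate is about 16%. At Week 52 it is (261/11)/52 = 23.7/52, so r = 0.68 and the rate is about 19%.

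**In kilograms.** Assume a Week 26 SD of 3.5 kg and 371 per arm. The correct SE is 3.5 × sqrt(2/371) = 0.257 kg. If the SD has doubled since Week 2, the literal model reports 0.753 × 0.257 = 0.194 kg.

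**Simulation check at Week 26** (REML compound-symmetry fit, 436 per arm, 15% monotone dropout, 300 runs per case)
- True compound symmetry: model SE / empirical SD 1.01, rejection 5.7%.
- Constant variance with decaying correlation: 1.05, rejection 5.0%.
- SD doubling with decaying correlation: 0.71, rejection 16.3%.

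The first two are within simulation error of no bias. The third agrees with the formula to within simulation error.

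**After the change.** Under unstructured errors the contrast uses that visit's own variance, so r = 1 and the error rate is 5% on every path.

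**The case against.** The strongest reply is that nothing has been changed. SAP 6.12.6 still calls the model an MMRM, does not say that a random patient factor is the only covariance term, and does not withdraw the protocol's structure. The phrase may simply identify the patient as the subject of the repeated measures, with Protocol 10.3.1 supplying the rest. Both documents require a change of method to be described and justified in the SAP or the study report, and neither the SAP text nor its revision history declares one.

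This stands as far as it goes. A reader might infer that the SAP has replaced unstructured covariance with compound symmetry; the documents do not establish that, because SAP 6.12.6 names no structure. But the charitable reading still leaves these variables without a stated structure in the SAP, and the only covariance term it does write down points elsewhere.

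A reader might also think that the two texts cannot be combined. They can. A random patient effect added to unstructured errors gives a sum that is itself unstructured. The split between the two parts is not identifiable and software may warn, but the fixed-effect standard errors would in principle be right. The bias arises only if the random factor stands alone.

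The stakes are also limited. Objectives 17 and 21 are exploratory. Neither the ANCOVA of the last available value nor the Fisher's exact comparison of weight changes of at least 7% depends on this covariance. That ANCOVA mixes early-discontinuation values with endpoint values, so it answers a somewhat different question and does not correct the MMRM's standard error.

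**Conclusion.** The mismatch in wording is real and worth correcting. Its consequence is conditional on two things: that SAP 6.12.6 is coded literally, and that the variance of weight change rises over visits. If both hold, the weight standard errors are about 10% too small when the SD rises by a quarter and about 25% too small when it doubles. The error rate is about 8% to 20% across the 1.25-fold to 3-fold range.

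A reader might infer that the weight standard errors are likely too small. The documents do not support that: they give no weight SD at any visit, constant variance gives no bias, and falling variance makes the standard error too large. Growing spread is plausible for weight change but undocumented.

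No bias is claimed for blood pressure or pulse. None has been calculated for antibody binding or lead-in insulin dose, where the case for changing the text is consistency only. No confirmatory conclusion of the trial is affected.

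**What to change.** In SAP 6.12.6, replace the random patient factor with unstructured within-patient errors with patient as the subject, using the fallback order and Kenward-Roger degrees of freedom of SAP 6.11.1, and no additional random patient effect. Make the same replacement in SAP 6.12.7.1 and 6.10, so that these MMRMs follow Protocol 10.3.1. If the sponsor intended a different structure, the SAP should name it and justify it.

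The cost is wording in three sections and a small change to the model code, with no new data. Weight intervals may widen, and the 52-week model with 11 post-randomization visits may need one of the listed fallback structures.

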6.12.7. Immunogenicity

Blood samples for immunogenicity testing will be collected to determine antibody production against insulin lispro for all enrolled patients since Visit 2 prior to the first dose of study-provided prandial insulin treatment. Therefore, the blood sample result at Visit 2 will be considered as the anti-insulin lispro level at baseline for this study.

Patients who complete the 4-week safety follow-up visit (Visit 801) and have treatment-emergent anti-insulin lispro antibodies that have not returned to prespecified baseline range (Visit 2) will be asked to participate in follow-up to monitor antibody levels. The assessment of immunogenicity will include analyses of treatment-emergent anti-insulin lispro antibody up to

Visit 801 and analyses of anti-insulin lispro antibody return to baseline during the insulin lispro antibody safety follow up period.

6.12.7.1. Treatment Emergent Anti-Insulin Lispro Antibody

The treatment-emergent anti-insulin lispro antibody (denoted as treatment-emergent antidrug antibody [TEADA] throughout this SAP) is based on the change from baseline (Visit 2) to postbaseline (post-Visit 2) in the anti-insulin lispro antibody level (percent binding). Treatment-emergent antidrug antibody can be sub-classified as either treatment-induced (not detected anti-insulin lispro antibody at baseline) or treatment-boosted (detected anti-insulin antibody at baseline):

- treatment-induced response: change from not detected anti-insulin lispro at baseline (Visit 2) to postbaseline detected anti-insulin lispro;
- treatment-boosted response: change from detected anti-insulin lispro at baseline (Visit 2) to postbaseline detected anti-insulin lispro antibody level (percent binding) at least 157% of the baseline value.

The TEADA status during a specific analysis period will be determined using all data in the corresponding analysis period regardless of IP use. The summary for TEADA status and the anti-insulin lispro antibody level will use the same analysis data.

The number and percentage of patients with positive TEADA response during the treatment period of 0 to 26 weeks will be summarized by treatment group. For patients with positive TEADA response during the treatment period of 0 to 26 weeks, the number and percentage of patients with positive insulin cross-reactivity anytime during the treatment period of 0 to 26 weeks will also be summarized by treatment group. Treatment groups will be compared by Fisher's exact test.

The above summary of TEADA response will be repeated for the analysis period of Visit 2 to Visit 801. The 2 double-blind treatment groups and the open-label treatment group will be summarized separately due to different duration of treatment period. For patients with positive TEADA response, the number and percentage of patients not meeting the TEADA criteria at Visit 801 will also be summarized.

Both actual and change from baseline (Visit 2) for the anti-insulin lispro antibody level in percent binding will be summarized by scheduled visit prespecified in the protocol for patients with positive TEADA response during the treatment period of 0 to 26 weeks. The repeated measurement from Visit 2 to Visit 18 will be analyzed by an MMRM model with treatment, baseline value of the response variable, visit, and visit by treatment interaction as fixed factors and patient as the random factor. The ANCOVA model using treatment and baseline value as covariates will be used for the analysis of maximum percent binding during the treatment period of 0 to 26 weeks. A similar summary of antibody level in percent binding during the analysis period of Visit 2 to Visit 801 will be generated separately for the 2 double-blind treatment groups and the open-label treatment group.

A listing of anti-insulin lispro antibody at each visit will be provided. The listing will include anti-insulin lispro antibody status (detected/not detected), anti-insulin lispro antibody percent binding, TEADA status (positive/negative), insulin cross-reactivity status, insulin cross-reactivity percent binding for the safety population.

Subgroup analysis for the following selected efficacy and safety variables will be performed by the TEADA status during the treatment period of 0 to 26 weeks:

- Use data prior to discontinuation of IP:
 - HbA1c and change from baseline in HbA1c
 - 1-hour and 2-hour PPG excursions
 - basal, prandial, and total insulin dose
 - event rate (per patient per year) of overall hypoglycemic events
- Use all data regardless of IP use:
 - treatment-emergent injection site reaction and hypersensitivity reaction

The analyses for HbA1c and change from baseline in HbA1c will be performed using an MMRM model for the primary analysis and the HbA1c data prior to discontinuation of IP. The model will include additional fixed terms of subgroup, subgroup by treatment interaction, subgroup by visit interaction, and 3-way interaction of treatment, subgroup, and visit.

The PPG excursions will be analyzed by the ANCOVA model same as the model specified in Section 6.11.2 using the efficacy estimand. The model will include additional terms of subgroup, subgroup by treatment interaction, subgroup by visit interaction, and 3-way interaction of treatment, subgroup, and visit.

The subgroup analysis for insulin dose will use the MMRM model specified in Section 6.11.5 using the efficacy estimand. The model will include additional fixed terms of subgroup, subgroup by treatment interaction, subgroup by visit interaction, and 3-way interaction of treatment, subgroup and visit.

The treatment emergent injection site reaction and hypersensitivity reaction will be analyzed by a logistic regression model including terms of treatment, subgroup, and treatment by subgroup interaction. All data regardless of IP use will be used for this analysis.

The negative binomial regression model specified in Table 6.6 with additional terms of subgroup, treatment by subgroup interaction will be used for the subgroup analysis of overall hypoglycemia event rate while on IP.

The interaction effects (3-way for MMRM and 2-way for ANCOVA/logistic regression model/negative binomial regression model) will be evaluated using a significance level of 0.10, unadjusted. If the interaction effect is significant ($p < 0.10$), separate analyses without the terms related to the subgroup will be performed for each subpopulation.

The above subgroup analyses may be repeated for the 2 double-blind treatment groups using the subgroup defined by TEADA status during the analysis period of Visit 2 to Visit 801.

